7.2.9 Compliance with the use of e-Diary

If the setting in the electronic diary are incorrect for a subject (e.g., Run-in settings applied during treatment period or vice-versa), then compliance with use of e-Diary will still be considered.

In these cases, if any questions were answered, the session will count as “data recorded in the [REDACTED] device”.

Compliance with the use of e-Diary is based on visit dates. See Section 7.1 for the definition of the study periods and period durations (days). Period duration will be calculated differently for completed subjects and discontinued subjects as defined in Section 7.1.

Of note, the Visit 2 morning session relates to the run-in period, so this session is considered in the total number of sessions expected during the run-in.

The evaluation of compliance per period (Run-in/Treatment Period) is done using the following formula:

$$\frac{\text{Total number of sessions in the treatment period with data recorded in eDiary}}{\text{Total number of sessions expected per Period}} \times 100\%$$

The following categories will be discerned for compliance:

- [0%-10%]
- (10%-20%]
- (20%-30%]
- (30%-40%]
- (40%-50%]
- (50%-60%]
- (60%-70%]
- (70%-80%]

- (80%-90%]
- (90%-100%]

7.2.10 Efficacy Variables

• Overview

All spirometry results will be graded by an independent reviewer at [REDACTED]. The grades after the Best Test Review are: U = Unacceptable, A = Acceptable, and B = Borderline Acceptable. All spirometry values, including the values scored with a grade “Unacceptable”, will be considered in the calculation of the derived variables. This follows the approach recommended by the paper by Hankinson et al. (Eur Respir J 2015), where it was concluded that quality assessment regarding the acceptability of individual blows should be primarily used as an aid to good quality during testing rather than a reason to subsequently disregard data.

Spirometry data together with the time of scheduled time points are imported from external [REDACTED] data. In case of historical reversibility data are reported in eCRF only.

In addition, the spirometry values excluded from the analysis based on the decisions taken during the Blind Data Review Meeting (e.g., due to technical issues) will be considered to be missing prior to the calculation of the derived variables. In the listings, these assessments will be shown and flagged, to highlight their exclusion from the analyses.

• Primary Efficacy Variable

The primary efficacy variable is the change from baseline in pre-dose morning FEV₁ at Week 8. The baseline value is the average of the T-45 and T-15 min pre-dose FEV₁ measurements on Day 1. FEV₁ is a continuous variable derived from spirometry data ([REDACTED]).

If one of the spirometry measurements at 45 min and 15 min pre-dose is not available, then the non-missing measurement will be taken as the pre-dose value. If no measurement is available, then the pre-dose value will be considered as missing.

In case of rescue medication intake on a visit day, all spirometry data recorded from the time of rescue medication intake onwards for 6 hours will be analyzed as part of the ITT Population with no exception, but they will be excluded from the analysis of primary efficacy endpoint for the PP population.

Secondary Efficacy Variables

In case of rescue medication intake on a visit day, all spirometry data recorded will be analyzed as part of the ITT Population with no exception.

For the derivations of secondary efficacy variables like, average use of rescue medication percentage of rescue medication-free days, daily asthma symptoms scores, number and percentage of asthma symptoms-free days, number and percentage of asthma control days, a minimum of 7 days with available measurements will be required for each inter-visit period (including the run-in period) to consider the variable as non-missing. For these variables, a

“day” is considered as the evening diary session (for which questions relate to the morning) and the following morning diary session (for which questions relate to the prior evening).

- *Change from baseline in pre-dose morning FEV₁ at Week 4*

FEV₁ is a continuous variable derived from spirometry data (■■■■). The baseline value is the average of the T-45 and T-15 min pre-dose FEV₁ measurements on Day 1.

If one of the spirometry measurements at 45 min and 15 min pre-dose is not available, then the non-missing measurement will be taken as the pre-dose value. If no measurement is available, then the pre-dose value will be considered as missing.

- *Change from baseline in pre-dose morning FVC at Week 4 and Week 8*

FVC is a continuous variable derived from spirometry data (■■■■). The baseline value is the average of the T-45 and T-15 min pre-dose FVC measurements on Day 1.

If one of the spirometry measurements at 45 min and 15 min pre-dose is not available, then the non-missing measurement will be taken as the pre-dose value. If no measurement is available, then the pre-dose value will be considered as missing.

- *Change from baseline in ACQ-7 score at Week 4 and Week 8*

The ACQ consists of 7 items: six simple self-administered questions referring to asthma control and rescue treatment usage with one week recall, and a seventh item consisting of the % predicted FEV₁ completed by clinic staff. Scoring uses a 7-point scale, with 0 indicating “totally controlled” and 6 indicating “severely uncontrolled”. The ACQ score will be calculated as the average of all 7 items.

ACQ mean score is recorded on ‘Asthma Control Questionnaire’ eCRF page. Baseline ACQ-7 score is the ACQ score recorded at Day 1, before randomization.

- *Change from baseline in average use of rescue medication (number of puffs/day) during inter-visit periods and entire treatment period*

Information on rescue medication use is collected in the subject- e-diary and in the eCRF at clinic. The change from baseline in the average use of rescue medication is a continuous variable. The average use of rescue medication is calculated as

$$\frac{\sum \text{Number of puffs of rescue medication taken}}{\text{Number of days with available data}}$$

In case of duplicates information reported at clinic and in diary, the greatest information will be used. The average use of rescue medication of the entire treatment period will be derived only if both inter-visit period are non-missing. See Section 7.1 for the definition of the inter-visit and entire treatment periods.

If only a single diary session is missing for a given day (evening session or morning session), then the non-missing session will be used. If both sessions are missing, the day will be considered as missing.

- *Change from baseline in percentage of rescue medication-free days during inter-visit periods and entire treatment period.*

Information on rescue medication use is collected in the subject-completed e-diary and in the eCRF at clinic. A patient is assumed to have used rescue medication if the answer to either of the following questions is >0:

- How many times did you take rescue medication during the nighttime/daytime?
- How many inhalations of rescue medication did you take during the nighttime/daytime?

In case of duplicates information reported at clinic and in diary, the greatest information will be used. The change from baseline in the percentage of rescue medication-free days is a continuous variable. The percentage of rescue medication-free days is calculated as

$$\frac{\text{Number of rescue medication – free days}}{\text{Number of days with available data}} \times 100\%$$

The percentage of rescue medication-free days during the entire treatment period will be derived only if both inter-visit period are non-missing. See Section 7.1 for the definition of the inter-visit and entire treatment periods.

If only a single diary session is missing for a given day (evening session or morning session), then the non-missing session will be used. If both sessions are missing, the day will be considered as missing.

- *Change from baseline in daily asthma symptoms scores during inter-visit periods and entire treatment period*

The change from baseline in daily asthma symptoms score is a continuous variable. Subjects have to record asthma symptom score (overall symptoms, cough, wheeze, chest tightness and breathlessness) in the morning (night-time asthma symptom score) and in the evening (daytime asthma symptom score). These data are collected on the subject's diary.

Daily asthma symptoms score are performed separately for morning score and evening score and also as a total, where the total equal the sum of the morning and evening scores.

The daily morning asthma symptoms score is calculate as

$$\frac{\sum \text{Daily Asthma Symptoms score (morning)}}{\text{Number of days with available data}}$$

where “Daily Asthma Symptoms scores (morning)” is considered separately for “Cough”, “Wheeze”, “Chest Tightness”, “Breathlessness” and “overall symptoms” morning individual scores.

Degree of each asthma symptoms is evaluated using a 4-point scale from 0 to 3: None (0), Mild (1), Moderate (2) and Severe (3).

Daily asthma symptoms score during the entire treatment period will be derived only if both inter-visit period are non-missing. See Section 7.1 for the definition of the inter-visit and entire treatment periods.

The daily evening asthma symptom score will be computed as defined for morning score using evening individual symptom scores.

For cough, wheeze, chest tightness, breathlessness, and overall symptoms scores, a day will be constituted by the data recorded in the evening session of that day plus the data recorded in the morning session of the next day.

For each day of the treatment period, for each symptom, the “daily symptom score” will be calculated as the mean of the evening symptom score of the day and morning symptoms score of the next day.

If one of the two sessions (evening or morning) associated with the day is missing, the daily symptom score will be calculated on the available session only.

- *Change from baseline in percentage of asthma symptoms-free days during inter-visit periods and entire treatment period*

The change from baseline in the percentage of asthma symptoms-free days is a continuous variable. The percentage of asthma symptoms-free days is calculated as

$$\frac{\text{Number of asthma symptoms – free days}}{\text{Number of days with available data}} \times 100\%$$

Asthma symptoms-free days is the number of days with a total asthma score = 0 (daily morning plus evening asthma score).

If only a single diary session is missing for a given day (evening session or morning session), then the non-missing session will be used. If both sessions are missing, the day will be considered as missing. The percentage of asthma symptoms-free days during the entire treatment period will be derived only if both inter-visit period are non-missing. See Section 7.1 for the definition of the inter-visit and entire treatment periods.

- *Change from baseline in percentage of asthma control days during inter-visit periods and entire treatment period*

The change from baseline in percentage of asthma control day is a continuous variable. The percentage of asthma control day is calculated as

$$\frac{\text{Number of asthma control days}}{\text{Number of days with available data}} \times 100\%$$

The derived variable of Asthma Control Days will be calculated according to the following definition:

*Days with a total daily morning + evening asthma score = 0
AND no rescue medication use.*

If only a single diary session is missing for a given day (evening session or morning session), then the non-missing session will be used. If both sessions are missing, the day will be considered as missing. The percentage of asthma control days -free days during the entire treatment period will be derived only if both inter-visit period are non-missing. See Section 7.1 for the definition of the inter-visit and entire treatment periods.

- *Change from baseline in morning and evening pre-dose PEF during inter-visit periods and entire treatment period*

PEF measurement is a continuous variable derived from an electronic peak flow meter. During each measurement session (morning or evening before the intake of the run-in ICS medication or study drug) the subject will perform 3 exhalations. Data will be recorded in the [REDACTED] device (e-diary). For analysis, the derived PEF to be used will be the highest value of the available PEF measurements for the given time point.

A minimum of 2 PEF values should be available at a given time point in order to calculate the derived PEF for analysis. Otherwise, if fewer than 2 PEF values are available for a given time point, that time point will be considered as missing for analysis of PEF. A minimum of 7 days with available measurements will be required for each inter-visit period (including the run-in period) to consider the morning and evening pre-dose PEF as non-missing. The morning and evening pre-dose PEF during the entire treatment period will be derived only if both inter-visit periods are non-missing. See Section 7.1 for the definition of the inter-visit and entire treatment periods.

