7.2.12 Subject Diaries

Using the ePRO diary (system details to be provided by selected vendor) dispensed at V1, and with time and date stamped, subjects will be instructed to:

- Enter a daily record of daytime and night-time **Asthma Symptom Score** (overall symptoms, cough, wheeze, chest tightness and breathlessness), as follows:
 - **Morning (night-time asthma symptom score):**
 - 0 No symptom
 - 1 Mild: symptoms not causing awakening
 - 2 Moderate: discomfort enough to cause awakenings
 - 3 Severe: causing awakenings for most of the night / do not allow to sleep at all
 - **Evening (daytime asthma symptom score):**
 - 0 No symptom
 - 1 Mild: aware of symptoms which can be easily tolerated
 - 2 Moderate: discomfort enough to cause interference with daily activity
 - 3 Severe: incapacitating with inability to work/take part in usual activity
- Record the daily use of **Asthma Rescue Medication** as follows: the number of puffs taken during the night will be recorded each morning on awakening, while the number of puffs taken during the day will be recorded each evening, both before taking the study drug

- The derived variable of **Asthma Control Days**[\[76\]](#) will be calculated according to the following definition:
 - Days (night-time plus daytime) with a total asthma score = 0
 - No rescue medication use.

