12.3.2 Missing data

- For the primary efficacy analysis, a linear mixed model for repeated measures will be used to handle missing data. Under the Missing At Random (MAR) assumption, this model provides an unbiased estimate of the treatment effect that would have been observed if all subjects had continued on treatment for the full study duration. This approach addresses efficacy (or de jure) hypotheses, estimating the causal effects of the initially randomized drug if taken as directed (in contrast with effectiveness, or de facto, hypotheses, evaluating the effect of the drug as actually taken).[\[77\]](#) The efficacy estimand is considered appropriate in the context of a phase II study aiming at characterising dose-response.[\[78\]](#)[\[79\]](#)[\[80\]](#)
- If one of the spirometry measurements at 45 min and 15 min pre-dose is not available, then the non-missing measurement will be taken as the pre-dose value. If no measurement is available, then the pre-dose value will be considered as missing.
- A minimum of 7 days with available measurements will be required for each inter-visit period (including run-in period) to consider the following variables as non-missing: average use of rescue medication, percentage of rescue medication-free days, daily asthma symptoms, and percentage of asthma symptom-free days, percentage of asthma control days, morning and evening PEF.
- For ACQ-7 questionnaire, the total score will be calculated only if all the scores derived from all the seven items are recorded.

Further details on dealing with missing data, along with the handling of possible outliers, will be described in the SAP. Other critical missing data, if any, will be discussed during the review of the data. Decisions will be fully documented in the Data Review Report.

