The approach described below will ensure that the least squares means calculated by SAS will be based on:

- coefficients for classification effects (i.e., the effects of categorical covariates) proportional to the margins observed in the group of subjects analysed;
- effects of quantitative covariates set equal to their mean values in the group of subjects analysed.

The analysis is based on the following steps:

1. generate a dataset by selecting:
 - in case of repeated post-randomisation measurements (e.g., FEV₁ at each visit, analysed using a linear mixed model for repeated measures): all the post-randomisation records for subjects with at least one available and valid post-randomisation measurement and no missing covariates;
2. in case of repeated post-randomisation measurements, add to the dataset generated in step 1 the records for missing post-randomisation visits of the subjects included in the dataset. In the added records the value of the response variable will be missing, but the full information on covariates has to be included;
3. use the dataset obtained as the input dataset for the MIXED procedure, specifying the following options in the LSMEANS statement:
 - in case of repeated post-randomisation measurements: OM AT MEANS;

Example: analysis of change from baseline (Visit 2) at all visits (Visits 3 to 5) based on a mixed model for repeated measures including the effects of treatment, visit (categorical variable), treatment by visit interaction, baseline and another covariate. Visit 1 represents the screening visit.

Original dataset (X = available value, . = missing or invalid value):

| Patient | Treatment | Covariate | Baseline | Visit | Change from baseline |
|---------|-----------|-----------|----------|-------|----------------------|
| 1 | A | X | X | 1 | . |
| 1 | A | X | X | 2 | . |
| 1 | A | X | X | 3 | X |
| 1 | A | X | X | 4 | X |
| 1 | A | X | X | 5 | X |
| 2 | B | X | X | 1 | . |
| 2 | B | X | X | 2 | . |
| 2 | B | X | X | 3 | X |
| 3 | A | X | X | 1 | . |
| 3 | A | X | X | 2 | . |
| 3 | A | X | X | 3 | X |
| 3 | A | X | X | 4 | . |
| 3 | A | X | X | 5 | X |
| 4 | B | X | X | 1 | . |
| 4 | B | X | X | 2 | . |
| 5 | A | . | X | 1 | . |
| 5 | A | . | X | 2 | . |
| 5 | A | . | X | 3 | X |

Step 1 (visits 1 and 2 not selected since pre-randomisation, subject 4 not selected due to missing post-randomisation measurements, subject 5 not selected due to missing covariate):

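### Average rescue use is understated because a diary day with one recorded session counts as a full day; the treatment difference is attenuated if such days are equally frequent across arms and biased in either direction otherwise

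*SAP*

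**What the plan says.** Protocol 7.2.12 splits rescue recording between two diary sessions: "the number of puffs taken during the night will be recorded each morning on awakening", and daytime puffs are entered in the evening. SAP 7.2.10 builds a diary day from the two; a day "is considered as the evening diary session (for which questions relate to the morning) and the following morning diary session".

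For average rescue use, SAP 7.2.10 gives a ratio. The numerator is the sum of "Number of puffs of rescue medication taken" and the denominator is "Number of days with available data". The rule for incomplete days is "If only a single diary session is missing for a given day (evening session or morning session), then the non-missing session will be used", and a day is missing only when neither session was recorded. If clinic and diary both report use, the larger value is taken.

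Protocol 12.3.2 sets the completeness threshold: "A minimum of 7 days with available measurements will be required for each inter-visit period (including run-in period") before a diary variable counts as non-missing. It does not say how a day with one session is to be weighted. SAP 7.1 takes the run-in result as the baseline for diary variables and gives no separate formula for it.

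**The concern.** The numerator is built from sessions and the denominator from days. When one session is missing, the puffs it would have held are lost from the numerator but the day stays in the denominator at full weight. In effect the missing half of the day is scored as zero puffs. SAP 7.2.10 states no rescaling, half-day weight or imputation.

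Elsewhere the SAP avoids this. The daily symptom score in the same section is a mean over whichever sessions exist, so it scales itself. SAP 7.2.8 removes sessions with wrong diary settings from both the numerator and the denominator of drug compliance.

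Change in puffs per day is a named secondary endpoint of a dose-ranging trial, where the size of the effect matters as well as its sign. The endpoint may be biased even if sessions are missed purely at random.

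**Working it through.** The documents state no figure for rescue use or diary completion, so there is no planned value to reproduce. Completion, clustering of misses and true use below are all assumptions.

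**1. One subject.** Take 28 days with 1 daytime and 1 night-time puff each, so the true average is 2.0 per day. If 7 days have only one session, the rule gives (21 × 2 + 7 × 1) / 28 = 49/28 = 1.75.

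**2. General factor.** Let m be the share of counted days with one session and s the share of daily puffs in the unrecorded session. The expected result is the true average × (1 − m·s). At m = 20% the factor is 0.96, 0.90 and 0.84 for s = 0.2, 0.5 and 0.8. If the two sessions are missed equally often, s averages 0.5 whatever the day/night split.

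**3. In terms of completion.** Let c be session completion and r the within-day correlation of misses.
- P(one session) = 2c(1−c)(1−r)
- P(none) = (1−c)² + r·c(1−c)
- Understatement u = 0.5 × P(one) / (1 − P(none))

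Example at c = 0.90, r = 0: 0.5 × 0.18 / 0.99 = 9.1%.

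| c | r = 0 | r = 0.5 | r = 1 |
|---|---|---|---|
| 0.95 | 4.8% | 2.4% | 0% |
| 0.90 | 9.1% | 4.8% | 0% |
| 0.80 | 16.7% | 9.1% | 0% |

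**4. Treatment difference, equal completion.** Assume true use of 3.00 on placebo and 2.25 on active, a difference of −0.75. Both means shrink by u, so the difference becomes −0.75 × (1 − u). With independent misses that is −0.71, −0.68 and about −0.63 at c = 0.95, 0.90 and 0.80. Simulation with baseline as covariate agrees to within 0.01, and averaging each session type separately returns about −0.75 throughout.

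**5. Treatment difference, unequal completion on treatment (independent misses).**
- Placebo 0.90, active 0.80: 2.25 × 0.8333 − 3.00 × 0.9091 = 1.875 − 2.727 = −0.85. The effect is overstated.
- Placebo 0.80, active 0.90: 2.25 × 0.9091 − 3.00 × 0.8333 = 2.0455 − 2.5000 = −0.4545, about −0.45. The effect is strongly understated.
- No true effect, 3.00 in both arms, completion 0.90 against 0.80: 3 × (0.9091 − 0.8333) = 0.23 puffs/day of spurious difference.

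The effect is overstated once the ratio of understatements, active to placebo, exceeds the ratio of true use, placebo to active: here 3.00/2.25 = 1.33.

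**6. Change within an arm.** With 2.0 puffs/day throughout and s = 0.5, let one-session days rise from 10% in run-in to 20% on treatment. The rule gives 1.90, then 1.80, a false fall of 0.10 in an arm where nothing changed.

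**The case against.** **The weight is inferred.** The SAP never says outright that a one-session day counts as 1, and SAP 5.2 leaves dataset specifications to a separate document. This stands as a caveat. The full-day reading is nonetheless the natural one, because a day leaves the count only when both sessions are missing.

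**The size is assumed.** This also stands. The plausible range includes zero, and at completion 0.95 with correlation 0.5 the difference moves only from −0.75 to −0.73. Protocol 7.2.12 provides alarms, daily transmission, portal checks and phone calls, which make poor completion less likely. They do not change the formula. The seven-day minimum can be met entirely by one-session days, and the duplicate rule cannot fill a session missing from both sources. The e-diary compliance tables (SAP 7.2.9, 10.5.3) count sessions overall, so they do not show how misses cluster within days. Blind review is a route to a correction but does not specify one.

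**A stronger reading.** A reader might infer that the treatment difference is always understated. The documents do not support that: it holds with similar frequencies of one-session days, and step 5 shows overstatement when completion is worse in the arm with lower use. With equal completion and no true effect, the rule produces no false difference.

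**Free-day endpoints.** A reader might also infer that rescue-free, symptom-free and asthma-control days need the same repair, since one session can qualify a day there too (for control days, "Days with a total daily morning + evening asthma score = 0" plus no rescue use). The levels rise, but the contrasts hardly move. With session-free probability q and independent sessions, the reported share at c = 0.90 is (0.81q² + 0.18q)/0.99. A true 13.0-point difference (q = 0.6 v 0.7) becomes 12.5, and a true 9.0 (0.4 v 0.5) becomes 9.2. No change is needed there.

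**Conclusion.** The rule as written gives too low a value for average puffs per day, baseline included, whenever one-session days occur and puffs were taken in the unrecorded session. This rests on the SAP's formula and on the inferred full-day weight. The direction of error in the treatment difference is conditional: attenuation if one-session days are about equally frequent across arms and periods, and bias either way if they are not. The size depends wholly on completion and clustering that the documents do not report; the range shown runs from 0 to 16.7% of the level.

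The flaw lies in the SAP derivation and does not contradict the protocol, which is silent on one-session days. It touches a secondary endpoint without multiplicity adjustment (SAP 8.2.1.4) and leaves the primary FEV1 analysis alone. Correction is worthwhile because it is cheap and can be settled before unblinding.

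**What to change.** Before unblinding, define average rescue use in each period, run-in included, as mean puffs over recorded daytime sessions plus mean puffs over recorded night-time sessions. Keep the existing minimum of seven days with data and add only a low minimum per session type, for example five of each.

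The cost is SAP wording, derivation code and a small loss of subjects. SAP 8.1 admits to the model only "subjects with at least one available and valid post-randomisation measurement and no missing covariates", so a lost baseline removes the subject from this analysis. For a 14-day run-in with independent misses and assumed between-subject SD of completion of 0.10 / 0.15, the loss is 0.3 / 2.1% of baselines at mean completion 0.90 and 0.6 / 2.8% at 0.80. The present rule loses under 1%. A 12-day run-in, which the visit window allows, would lose more. Requiring seven of each session type is not advised: on the same assumptions it loses 1.6 / 5.0% and 4.2 / 9.0%.

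The alternative is to state that a one-session day counts as half a day in the denominator. This needs no new exclusions and is exact if daytime and night-time use are equal or if the two sessions are missed equally often.
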